Subjects will be recruited via Flyers posted on Campus and/or in Obstetrics and Gynecology practices and/or via ads posted on Craigslist by research coordinator, [name]. From these ads, interested individuals will be asked to go on Survey Monkey (<https://www.surveymonkey.com/r/HPENlabresearch>) and complete a survey that will help us determine whether they meet our selection criteria or email [name] at [[contact]](mailto:[contact]) or call the research team. Research coordinator will then contact individuals who may meet selection criteria. She and [name] and/or [name] will meet with them and give them the informed consent to read and go through it with the subjects. Upon receipt of a signed informed consent, participants will meet with [name] or [name] who will diagnose them with HSDD. If the subject does not have HSDD, she is not eligible to participate in the study. Subjects with a confirmed diagnosis of HSDD by [name] or [name] will then be randomly assigned by the UChicago Pharmacy/Investigational Drug Service to either Addyi (100 mg once daily at bedtime for 8 weeks, n = 60 subjects) or placebo (100 mg once daily at bedtime for 8 weeks, n = 60 subjects). The research question of this double-blind randomized outpatient clinical trial is to determine the pre-post change in the Flibanserin group and investigate the

extent to which Flibanserin normalizes brain activity in women with HSDD and the extent to which regional brain activation is associated with changes in symptoms and behavior (as measured with self-report measures of sexual desire and/or eye-tracking movements).

The study is registered on clinicaltrials.gov.

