## **9. Experimental Controls:**

We will recruit 60 pre-menopausal women and 60 postmenopausal women who have HSDD, as determined by one of the MDs on the research team (using the DSM 5 criteria), during Visit 1. Then, the pharmacist will randomly assign the subjects to the treatment group (group with Flibanserin) or to the control group (group with placebo).

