## **10. Type and Number of Experimental Subjects:**

We expect to collect data from a total of 120 subjects between the age of 21 and 74 years. We will be testing premenopausal and postmenopausal women with hypoactive sexual desire disorder. Flibanserin is FDA approved for premenopausal but not postmenopausal women with HSDD. Women who are pregnant (or think they are pregnant), or who are nursing (or breastfeeding), or women who report not being able to stop drinking alcohol during the duration of the study will NOT be tested.

**Power:** Using G\* power calculation software (Version 3.1.9.2) for a within-between interaction in repeated measures ANOVA, a total sample size of 120 will yield 95% power to detect a significance, with alpha = .05 and an effect size of 0.14.

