**Statistical Hypotheses:**

a. The research questions of this double-blind randomized study are: (a) to determine the pre-post change in the Flibanserin group vs. Placebo group in women with hypoactive sexual desire disorder (HSDD), (b) to compare the effect is Flibanserin (vs. placebo) on behavioral and brain changes between pre-menopausal women and postmenopausal women, (c) to investigate the extent to which post-Flibanserin's regional brain activations (compared to pre-Flibanserin's regional brain activations) are associated with changes in symptoms and behavior (as measured with self-report measures of sexual desire and/or eye-tracking movements), and (d) to investigate the extent to which Flibanserin normalizes brain activity in women with HSDD compared to matched healthy controls. The statistical hypotheses include the following:

i. Demographics: Statistical analyses for demographic and self-report measures will be computed using SPSS software. Prior to inferential analyses, descriptive statistics, including distributions, means, standard deviations, skewness, and kurtosis will be generated. Data will also be examined for the pattern and mechanism of missing data. Continuous data will be tested for normality and homogeneity of variance. Potential differences between the treatment and placebo groups in terms of demographic and behavioral measures will be explored using multivariate analysis of variance (MANOVA) or appropriate non-parametric tests as appropriate. Similar analyses will be performed to detect potential differences between the pre-menopausal subjects and the post-menopausal subjects. The overall significance level for these analyses will be at 5%, and effect sizes and confidence intervals will also be performed to test hypotheses about correlations.

ii. Behavioral data: Statistical analyses will be computed using SPSS software. Reaction times and performance data (ratings) will be screened. Prior to inferential analyses, descriptive statistics, including distributions, means, standard deviations, skewness, and kurtosis will be generated. Data will also be examined for the pattern

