and mechanism of missing data. A 2 (Treatment Type: Addyi or Placebo) x 2 (Group Type: pre- or post-menopausal) X 2 (type of stimuli: desired, nondesired) x 3 time (Visit 1, Visit 2, Visit 3) repeated-measures ANOVA will be performed on the reaction times and ratings to assess for main effects and interaction effects. P values, confidence interval, and effect sizes will be reported.

iii. Eye-tracking Data: A similar ANOVA will be performed for the following dependent variables: onset to first fixation and duration of fixation. As in our 2014's paper (Bolmont, Cacioppo, & Cacioppo), we will also analyzed include the subjects' visual area of interest (face vs. body) as a within-subject factors in our ANOVA.

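### The behavioural and eye-tracking ANOVAs report p values for every main effect and interaction but never name the term that tests the drug, leaving about a 19% (behavioural) or 34% (eye-tracking) chance per variable of a false-positive treatment-by-time term.

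*Combined protocol and SAP*

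**What the plan says.** Section 11, Statistical Hypotheses, item ii crosses treatment (2 levels), menopausal group (2), stimulus type (2) and visit (3) in a repeated-measures ANOVA. It is run on reaction times and on ratings "to assess for main effects and interaction effects", and p values, confidence intervals and effect sizes are to be reported.

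The eye-tracking item then states: "A similar ANOVA will be performed for the following dependent variables: onset to first fixation and duration of fixation". It adds area of interest (face or body) as a within-subject factor.

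Neither item names a term as the drug test, ranks the terms, gives a significance level or mentions adjustment. Two other places give a level:

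- Item i (Demographics) states "The overall significance level for these analyses will be at 5" per cent for its own comparisons and names no method of control.
- The power statement in section 10 works "with alpha = .05 and an effect size of 0.14".

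The opening of Statistical Hypotheses does pose the questions of interest: (a) pre-post change on flibanserin against placebo, and (b) whether the drug effect differs between pre- and postmenopausal women. It does not link either question to an ANOVA term.

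**The concern.** A full factorial ANOVA produces many F tests that involve treatment. If none is designated in advance, whichever falls below 0.05 can be presented as a flibanserin effect on behaviour or gaze, including a four- or five-way interaction that nobody predicted.

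The outcomes matter to the trial's claims. Aim 1 covers neurobehavioural responses, question (b) compares behavioural changes by menopausal group, and eye movement is the first secondary outcome listed. A chance interaction involving menopausal group could be read as evidence about postmenopausal women, for whom section 5 notes that the drug is not FDA approved.

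**Working it through.** **Inputs**

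- Sample: 120 women. Section 9 says "We will recruit 60 pre-menopausal women and 60 postmenopausal women who have HSDD", and section 5 gives 60 per treatment arm. I assume 30 per treatment-by-menopause cell.
- Factors: four for each of two behavioural variables, five for each of two eye-tracking variables (section 11).
- Alpha: 0.05 per F test. This is assumed, because the ANOVA items state none; section 10 gives .05 for the power calculation only.
- Effect size for costing: d = 0.48, the threshold in section 11 for a meaningful change relative to placebo.

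**1. The plan's own figure.** Section 10 says "a total sample size of 120 will yield 95% power to detect a significance", "for a within-between interaction in repeated measures ANOVA". Read 0.14 as Cohen's f and take 4 groups, 6 measurements (2 stimuli x 3 visits), correlation 0.5 and sphericity; none of these settings is stated.

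- Noncentrality = N f² m/(1 − rho) = 120 x 0.0196 x 6/0.5 = 28.2, on 15 and 580 df.
- Power = 94.8%, which agrees with the stated 95%.
- At the same correlation, 2 groups x 4 measurements gives 96.5%, 2 x 3 gives 92.7% and 4 x 3 gives 80.4%.

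More than one layout comes close to 95%, so the power statement does not reveal which term is meant as the drug test.

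**2. Counting terms**

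| Layout | All effects | Containing treatment | Containing treatment and time |
|---|---|---|---|
| Four factors | 2⁴ − 1 = 15 | 2³ = 8 | 2² = 4 |
| Five factors | 2⁵ − 1 = 31 | 2⁴ = 16 | 2³ = 8 |

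**3. Chance of at least one p < 0.05 when nothing is true.** Treating the F tests as independent, this is 1 − 0.95^k:

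- Treatment-by-time terms: 1 − 0.95⁴ = 18.5%; 1 − 0.95⁸ = 33.7%.
- All terms containing treatment: 1 − 0.95⁸ = 33.7%; 1 − 0.95¹⁶ = 56.0%.

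**4. Check by simulation.** Null mixed ANOVAs with 30 per cell, including the error terms that the tests share (20,000 runs with equal correlations, 10,000 for each non-spherical case):

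| Data | Treatment-by-time: four / five factors | All treatment terms: four / five factors |
|---|---|---|
| Equal correlations | 18.8% / 33.7% | 33.8% / 55.8% |
| Mildly non-spherical, uncorrected | 21.5% / 39.1% | 34.9% / 57.5% |
| Strongly non-spherical, uncorrected | 26.9% / 46.0% | 30.8% / 51.1% |

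The independence formula is adequate under sphericity. If sphericity fails and is not corrected, the treatment-by-time rates rise. With one designated test per variable, the rate is 5% per variable.

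**5. Cost of adjusting across four variables.** Two-sample t test, 60 per arm, d = 0.48; noncentrality = 0.48 x √(60/2) = 2.63.

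- Alpha 0.05: power 74%.
- Alpha 0.05/4 = 0.0125 (strictest Holm step): power 54%.

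**The case against.** The strongest reply is that the plan is less open than the ANOVA items suggest. Questions (a) and (b) point to treatment-by-time and its interaction with menopausal group. Confidence intervals and effect sizes are required alongside p values, and section 11 sets effect-size thresholds for meaningful change, including relationships with reaction time and eye movement. This stands in part: what is missing is the link between question and term, and the plan does not invite every term to be claimed. But nothing restricts the claims, and even the treatment-by-time terms alone carry 19% and 34%.

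A second reply is that item i's overall 5% level extends to these data, since its comparisons include behavioural measures. That is ambiguous. Even if it does, no method is given that would hold an overall level.

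A third reply is that these are supporting outcomes, for which unadjusted analysis is common. This also stands. Eye tracking is secondary, and reaction times and ratings are not in the outcome lists. It argues against mandatory adjustment, but naming the drug test is still needed.

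Two stronger readings are tempting, and the documents do not support them:

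- A reader might infer that a chance drug finding arises in 34% or 56% of analyses. Those figures include treatment terms without time, which average in the pre-dose Visit 1 and so give at best a diluted drug effect. They do not match the pre-post question.
- A reader might multiply across all four variables, 8 + 8 + 16 + 16 = 48 terms, to reach 1 − 0.95⁴⁸ = 91%. That adds independence between variables measured in the same women and again counts the terms without time.

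**Conclusion.** The concern holds for the behavioural and eye-tracking analyses. The plan does not name the term that tests the drug, and the chance of at least one false-positive treatment-by-time term is about 19% per behavioural variable and 34% per eye-tracking variable. Counting every treatment-containing term gives about 34% and 56%, as an outer figure.

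These rates assume 0.05 per F test, no true effects, sphericity, and face/body fully crossed with the other factors. The eye-tracking sentence is garbled and says only that face/body is a within-subject factor, so that last assumption affects the 34% and 56% for eye tracking.

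A reader might infer that the primary result is compromised. It is not: the primary outcome is the EEG evoked potential, which these ANOVAs do not analyse.

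**What to change.** Replace the general purpose in section 11, items ii and iii (eye-tracking), with these rules:

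1. **Drug effect (Aim 1).** For each of the four variables, name one test: flibanserin against placebo on the Visit 1 to Visit 3 (8-week) change in the desired-minus-nondesired difference. State that it is estimated in all women and also shown for postmenopausal women, on whom Aim 1 is framed.
2. **Menopausal group (Aim 2).** Report the treatment x time x menopausal-group contrast as an estimate with a confidence interval. Aim 2 predicts similarity, so a non-significant p value must not be read as support. For the same reason a Holm penalty does not suit this contrast: it makes non-significance, and hence a claim of similarity, easier.
3. **Everything else.** Label all other terms exploratory, with no significance claim. This includes area-of-interest interactions and treatment terms that average over pre-dose Visit 1.
4. **Sphericity.** State the correction for any three-visit F test that is still reported.

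The cost is wording only. Adjustment across the four variables (Holm or Benjamini-Hochberg) is optional for these supporting outcomes. It should be costed at the plan's own d = 0.48, where power falls from about 74% to 54% at the strictest Holm step. Costing it at 0.66 SD, where 60 per arm gives 95% power, shows a fall only to 86%, but 0.66 appears nowhere in the documents. If no adjustment is made, say so, and report the four designated tests together.

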## **4. Primary Outcome Measure:**

EEG Results: Evoked Brain Potentials (measured brain response that is the direct result of a specific cognitive event). We will be analyzing change from baseline EEG results at 8 weeks (before and after the subject takes the flibanserin or placebo). We will average the electrical brain activity evoked by each type of stimuli to calculate the evoked brain potentials (any stereotyped electrophysiological response to a stimulus).

Evoked brain potentials in response to sexually desired stimuli compared to:

1. Non sexually desired stimuli
2. Basic visual non-sexual stimuli (reversal checkerboard) will be our proposed endpoints, as they will allow us to measure electric brain signals specific to cognitive

mechanisms underlying sexual stimuli processing rather than any other non-cognitive processes or basic visual processes. Amplitude of the signal, latency, and brain topography across 128 recorded vectors will be measured.

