### **Secondary Outcome Measures:**

- Eye movement tracking: movements to first saccades. We will be analyzing change from baseline eye movement tracking results at 8 weeks.
- Female Sexual Function Index: change from baseline to final score at 8 weeks.
- UCLA Loneliness Scale: change from baseline to final score at 8 weeks.
- Life Satisfaction Scale: change from baseline to final score at 8 weeks.
- Body Dysmorphic Disorder Questionnaire: change in answers from baseline to final visit at 8 weeks.
- Hamilton Anxiety and Depression Scale: change from baseline to final score at 8 weeks.
- Rosenberg Self-Esteem Scale: change from baseline to final score at 8 weeks.
- Hostility Measure: change from baseline to final score at 8 weeks.
- Female Sexual Distress Scale-Revised: change from baseline to final score at 8 weeks.
- IOS Scale with Partner: change in answers from baseline to final answers at 8 weeks.
- Body image measure: change in baseline to final score at 8 weeks.
- Sexual Desire Inventory: change in baseline to final score at 8 weeks.
- Marital Satisfaction Scale: change in baseline to final score at 8 weeks.

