iii. Electrophysiological Data: EEG data will be analyzed using an established Matlab toolbox, CENA (The Chicago Electrical Neuroimaging Analytics). Standard statistical analyses will be performed using SPSS. Compared to fMRI, which has a very low temporal resolution, high-density EEG/ERP has a very high temporal resolution ([name] & Bianchi-Demicheli, 2008). When combined with brain source localization algorithms, high-density EEG-ERP is called electrical neuroimaging. Electrical neuroimaging can identify dynamical patterns of communication between brain regions that contrast analyses, such as fMRI, may not detect. This proposal takes advantage of electrical neuroimaging and a new suite of tools (i.e., the Chicago Electrical Neuroimaging Analytics, CENA), that [name] developed and validated recently for segmenting high-density electrical brain activity (Cacioppo et al., 2014, 2015). Compared to the standard waveform analysis of event-related potentials (ERP) components that provide local information about amplitude and latency of the brain electric signal collected from one electrode in response to a stimulus, CENA provides general information about the stable momentary configuration of the global scalp electric potential over a high-density multi-channel electrode array. This approach provides information about the temporal sequence of discrete information processing operations evoked by the presentation of a stimulus within the context of a particular experimental task. That temporal sequence of information processing includes a series of stable brain microstates, each of which is characterized by specific cognitive computations and a relatively stable spatial distribution of brain activity. Combined with brain source localization algorithms, this method can then provide a video-clip of the

potential brain sources that sustain every electrical brain state recorded from the surface of the scalp –without having to perform an fMRI scan (see attached example). The brain microstate approach complements the traditional approach of ERP peaks and troughs at specific electrode positions, but with more comprehensive analyses of time-varying activity across the entire scalp (Cacioppo et al., 2014, 2015).

A significant and clinically meaningful change from baseline for each subject pre- and post-treatment with flibanserin is as follows:

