Median effective doses of flibanserin on increase in SD level will demonstrate at least a medium effect size (e.g., Cohen's  $d > 0.48$ ) relative to placebo (PBO); and at least a medium effect size (Cohen's  $d > 0.48$ ) between flibanserin and PBO conditions in SD levels; and relationship between change in SD self-report levels and change in behavioral responses (reaction times) during SD paradigm in flibanserin (vs PBO) is of at least a medium effect size ( $r > 0.48$ ); or relationship between change in flibanserin and change in electrophysiological responses during SD paradigms in flibanserin (vs. PBO) is of at least a medium effect size ( $r > 0.48$ ); Relationship between change in Flibanserin and change in eye movement responses during SD paradigms in Flibanserin(vs. PBO) is of at least a medium effect size ( $r > 0.48$ ). There will be no adverse events of more than mild severity which are rated as possibly, probably, or definitely related to acute, oral administration of flibanserin to a greater extent than PBO in HSDD participants.

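### The plan's only numerical rule for a meaningful change does not require a drug-placebo difference in the primary EEG outcome

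*Combined protocol and SAP*

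**What the plan says.** Section 4 gives a single primary outcome, evoked brain potentials: "We will be analyzing change from baseline EEG results at 8 weeks". Responses to desired stimuli are to be compared with non-desired stimuli and with a reversal checkerboard. Several parameters are listed, and none is singled out: "Amplitude of the signal, latency, and brain topography across 128 recorded vectors will be measured".

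The self-report scales are secondary, among them "Sexual Desire Inventory: change in baseline to final score at 8 weeks".

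In Section 11, under Statistical Hypotheses, the Electrophysiological Data item ends with a definition introduced as "A significant and clinically meaningful change from baseline for each subject pre- and post-treatment with flibanserin is as follows". Its clauses are, in order:

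- A. "Median effective doses of flibanserin on increase in SD level will demonstrate at least a medium effect size" (Cohen's d > 0.48, relative to placebo).
- B. Joined by 'and': at least the same d "between flibanserin and PBO conditions in SD levels".
- C. Joined by 'and': r > 0.48 between change in self-reported SD and change in reaction times.
- D. Introduced by 'or': r > 0.48 for the "relationship between change in flibanserin and change in electrophysiological responses during SD paradigms in flibanserin (vs. PBO").
- E. With no connective: r > 0.48 for the corresponding relationship with eye movements.
- Safety: no excess over placebo of drug-related adverse events above mild severity.

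SD is never expanded. Clause C speaks of self-report, so it is read here as self-reported sexual desire.

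**The concern.** A rule that says when the trial has shown a meaningful change should turn on the outcome named as primary. Here the two clauses that clearly compare the arms are on a secondary outcome. The primary outcome appears once, as a relationship that another clause can replace. The purpose in Section 2 includes finding out how far flibanserin normalizes brain activity. Under this rule a meaningful change could be declared when the arms do not differ on EEG, and a substantial EEG difference could go unrecognised. Nothing else in Section 11 fills the gap. It sets out an ANOVA for reaction times and ratings and a similar one for eye-tracking, but for EEG it names only the software.

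**Working it through.** **Inputs.** 60 women per arm (Section 5). Total 120, alpha 0.05, power 95%, effect size 0.14, within-between interaction in repeated-measures ANOVA (Section 10). Thresholds d > 0.48 and r > 0.48 (Section 11). The documents give no expected EEG or desire effect, so every true effect below is an assumption.

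**1. The plan's own power figure.** With noncentrality λ = f²·N·m/(1 − ρ), 4 groups, m = 6 measurements (2 stimuli × 3 visits) and ρ = 0.5 (the last three not stated in Section 10): λ = 0.14² × 120 × 6/0.5 = 28.2, df 15 and 580, power 94.8%. The stated 95% can be reproduced. Section 10 does not say which outcome it covers, so it neither supports nor weakens this point.

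**2. Clause logic.** The wording allows several groupings. Suppose EEG change is identical in both arms and unrelated to anything else, so that D fails.

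| Grouping | Can it be met with D false? |
|---|---|
| (i) A and B and (C or D) and E | Yes, through A, B, C, E |
| (ii) (A and B and C) or D | Yes, through A, B, C |
| (iii) A and B and (C or D or E) | Yes, through A, B and either C or E |
| (iv) (A and B and C) or (D and E) | Yes, through A, B, C |

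The finding rests on this table. The remaining figures are illustrations.

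**3. Simulation of the efficacy clauses.** 20,000 trials, 60 per arm, thresholds applied to observed estimates, A and B treated as one d clause, safety clause left out.

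- No EEG effect, desire d = 0.8, reaction-time and eye-movement correlations 0.65: the clauses are met in 90.9%, 93.2%, 95.6% and 93.2% of trials for (i) to (iv).
- EEG d from 0.8 to 1.5, desire d = 0.2, all correlations 0.2, D taken as a within-arm correlation of EEG change with desire change: met in at most 1.0% of trials on any grouping.

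**4. The other reading of D.** D could mean the correlation of treatment assignment with EEG change. With equal arms r = d/√(d² + 4), so r = 0.48 corresponds to d = 2 × 0.48/√(1 − 0.48²) = 0.96/0.877 = 1.09. An EEG d of 0.8 gives r = 0.37 and 1.0 gives r = 0.45, both short of the threshold. If D also suffices alone (grouping ii), the rule is met in 6.9%, 32.4%, 70.7% and 98.0% of trials at true EEG d of 0.8, 1.0, 1.2 and 1.5. On (i) and (iv) it is still met in under 1%. On (iii) it cannot exceed the 6–7% chance of meeting the d clause.

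**5. One d clause alone.** From the noncentral t with 118 df, noncentrality d√30 and cut-off 0.48√30 = 2.63: P(observed d > 0.48) = 0.743 at true d = 0.6 and 0.066 at true d = 0.2.

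**6. Power if an EEG clause is added.** Two-sided 5% test of one change score, normal approximation: Φ(0.48√(60/2) − 1.96) = Φ(0.67) = 0.748. The d detectable with 95% power is (1.960 + 1.645)√(2/60) = 0.66. For 95% power at d = 0.48, n = 2(1.960 + 1.645)²/0.48² = 113 per arm.

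**The case against.** The strongest reply concerns clause D. Unlike C, it does not mention self-report. It names one measured variable, EEG change, and sets it against flibanserin versus placebo. Taken literally it may be a between-arm EEG clause expressed as r. That stands as a possible reading. A reader might infer that the EEG difference carries no weight at all, or could never alter the conclusion. The text does not support that: if D means treatment against EEG change and suffices alone, a very large EEG effect meets the rule. Nor are all the effect-size clauses about desire, since the r clauses carry the same label; only the two Cohen's d clauses are.

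It can also be said that defining the undefined term in D and making D mandatory would bring EEG into the rule. That is true, but it would be a substantive change, since the text makes D an alternative, and it would demand an EEG d above 1.09 where desire needs only 0.48.

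Thirdly, the plan calls this a meaningful change and does not call it a success criterion. In a desire disorder, clinical meaning may fairly rest on desire; Aim 1 names subjective feelings and neurobehavioral responses together. Nothing says the rule replaces reporting of the EEG result. This limits the point, but the rule sits in the EEG item, is mostly stated at group level against placebo, and has no counterpart for EEG in the text available (Sections 7 and 19 are not in it).

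Finally, 0.74 and 0.07 might be read as chances of meeting the whole rule. They are not. If the true correlation for C were 0.3 or 0.4, an observed r above 0.48 with 60 women would occur about 5% or 23% of the time. Multiplied by 0.743, assuming independence, that gives about 4% or 17%, before the eye-movement and safety clauses.

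**Conclusion.** The point holds in this form: the rule and the primary outcome do not match. The efficacy clauses can be satisfied with no drug-placebo EEG difference on all four groupings examined, which follows from the wording and needs no assumed effect size. The converse is slightly weaker: an EEG effect of around d = 0.8 with little effect on desire would normally fail, except by chance or on the one reading where D relates treatment to EEG change and stands alone, with an observed d above about 1.09. The safety clause can block the conclusion whatever the EEG shows. How often any of this would happen cannot be derived from the documents. The conclusion rests on SD meaning self-reported desire. Because a stated rule could support the wrong main conclusion, it should be reconciled with Section 4 before unblinding.

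**What to change.** Reconcile the closing paragraphs of the Electrophysiological Data item in Section 11 with Section 4:

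- Make the first, mandatory clause the flibanserin-minus-placebo difference in baseline-to-week-8 change in one named EEG parameter for one named contrast, with the direction of improvement fixed in advance. Desired minus non-desired stimuli could be the contrast, with the checkerboard comparison as supportive. Section 4 as it stands offers two comparators and amplitude, latency and topography over 128 channels, so the clause cannot be applied until a choice is made.
- Label the SD-level clauses key secondary, on a named scale such as the Sexual Desire Inventory.
- Treat the correlation clauses as mechanistic support, and define both variables in each.
- If desire is meant to decide the trial, name it primary in Section 4 instead and call EEG the mechanistic secondary.

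The cost is rewording in Sections 4 and 11, with no new data or patients. The downside, which the plan should state, is the roughly 75% power of a single EEG comparison at an assumed d of 0.48, below the 95% quoted in Section 10 for its own interaction test.

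### Computed within the flibanserin arm, the r > 0.48 clause linking change in desire to change in reaction time does not respond to the mean drug effect, so it cannot show one

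*Combined protocol and SAP*

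**What the plan says.** Section 11, under Statistical Hypotheses, introduces its criterion with "A significant and clinically meaningful change from baseline for each subject pre- and post-treatment with flibanserin is as follows". A list follows.

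- Two clauses require Cohen's d > 0.48. One is a comparison "between flibanserin and PBO conditions in SD levels".
- Three clauses require r > 0.48:
  - reaction time: "relationship between change in SD self-report levels and change in behavioral responses (reaction times) during SD paradigm in flibanserin (vs PBO");
  - EEG: "relationship between change in flibanserin and change in electrophysiological responses during SD paradigms in flibanserin (vs. PBO");
  - gaze: "Relationship between change in Flibanserin and change in eye movement responses during SD paradigms".

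The reaction-time clause is joined to the d clauses by an and, the EEG clause by an or, and the gaze clause by no connective. The plan does not say whether r is computed within the flibanserin arm, over both arms pooled, or as a difference between arms. It does not define a change in flibanserin, and Section 5 gives a single fixed dose.

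Research question (c) in the same section asks how far changes in regional activation "are associated with changes in symptoms and behavior". The r clauses are the only numerical criterion for that question. The planned repeated-measures ANOVAs for reaction time, ratings and gaze analyse each measure separately.

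**The concern.** A correlation between two change scores describes how women differ from one another. Adding the same amount to every woman's change leaves it exactly as it was. If r is taken within the flibanserin arm, the average benefit of the drug therefore drops out, and what remains is co-variation that can also be present on placebo. Adding a comparison with placebo in brackets does not cure this, because the clause gives one threshold for one r and no placebo value or contrast.

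At stake is the mechanistic conclusion. The clause could be reported as met when flibanserin does nothing, or as missed when it works through the measured response.

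**Working it through.** **Plan's own figures.** The plan gives no operating characteristic for the r clauses. Its only power figure (Section 10: N = 120, alpha 0.05, effect size 0.14, power 95%) is for an ANOVA interaction. Taking 0.14 as Cohen's f and assuming 4 groups, 6 repeated measures and correlation 0.5, the noncentrality is 120 × 6 × 0.14² / (1 − 0.5) = 28.2 on 15 and 580 df, giving 94.8%. It can be reproduced under those assumptions but does not bear on the r clauses.

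**Inputs.** From the documents: 60 per arm (Section 5) and threshold 0.48 (Section 11). Assumed, because the documents give none: bivariate normal change scores with SD 1, the same true correlation rho in both arms (0.30, 0.48, 0.60), and both changes scored so that the expected r is positive. The mean drug effect d, in SD units, is added to both changes. Each cell has 20,000 simulated trials.

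**Step 1: probability that the clause passes, by reading, uniform effect.**

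| Reading | d | rho 0.30 | rho 0.48 | rho 0.60 |
|---|---|---|---|---|
| r within flibanserin arm | 0 | 5.4% | 51.5% | 90.8% |
| | 0.8 | 5.3% | 51.4% | 90.6% |
| | 2.0 | 5.6% | 50.9% | 90.8% |
| r pooled over arms | 0 | 1.2% | 51.7% | 96.9% |
| | 0.8 | 13.7% | 86.4% | 99.8% |
| | 2.0 | 99.9% | 100% | 100% |
| r(flibanserin) − r(placebo) > 0.48 | 0 | 0.2% | 0.04% | 0.01% |
| | 0.8 | 0.2% | 0.05% | 0.01% |
| | 2.0 | 0.2% | 0.04% | 0.01% |

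**Step 2: analytic check of the within-arm row.** By Fisher's z, P(r > 0.48) = P(Z > [atanh 0.48 − atanh rho] × √57). At rho 0.30, (0.523 − 0.310) × 7.55 = 1.61, giving 5.4%. At 0.48 it is 0, giving 50%. At 0.60, (0.523 − 0.693) × 7.55 = −1.28, giving 90%. The mean effect d does not enter the formula.

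**Step 3: why the pooled r moves.** Its true value is (rho + d²/4) / (1 + d²/4). At rho 0.30 and d = 1.2 this is 0.66 / 1.36 = 0.485, and the simulated pass rate is 54.5%. When a 0.6 SD shift in the response carries through to desire, the pooled clause passes 2%, 60% and 99% of the time at the three rho values, against about 1%, 50% and 97% for an inert drug. At that effect size rho decides the result far more than the drug does.

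**Step 4: individual effects that vary.** Let each woman's drug effect have SD tau and act on both measures. The within-arm correlation becomes (rho + tau²) / (1 + tau²). At rho 0.30 and tau 0.8 this is 0.94 / 1.64 = 0.573. With mean effect 0.8 the pass rate rises from 5.7% at tau 0 to 84% at tau 0.8. At tau 0.8 it is about 85% whether the mean effect is 0 or 0.8. The clause responds to the spread of effects, not to their mean.

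**Step 5: EEG and gaze clauses.** If change in flibanserin means treatment versus placebo, r is a point-biserial correlation and depends directly on the drug effect. The pass rate is 0%, 7.7%, 73% and 100% at d = 0, 0.8, 1.2 and 2.0. With equal arms r = 0.48 corresponds to d = 2 × 0.48 / √(1 − 0.48²) = 1.09. If the term means change in desire on flibanserin, Steps 1 to 4 apply.

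**Step 6: would an indirect effect alone do instead?** Take a test that requires both an arm difference in the response and an arm-adjusted slope of desire on the response, with a 0.6 SD response shift. It rejects about 82–91% of the time over the three rho values, whether the drug raises desire through the response, leaves desire unchanged, or lowers it by 0.6 SD. It does not depend on the total effect on desire.

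**The case against.** The strongest case on the other side has four parts.

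- *The text allows a reading that responds to the drug.* It does, and this stands: a pooled r moves with the effect, as does a treatment-indicator r for EEG and gaze. A reader might infer that all three r clauses are blind to the drug. The documents do not support that, because only the reaction-time clause names change in desire as one of its variables.
- *A correlation suits a between-woman question.* Research question (c) asks about association, and if responses vary between women the within-arm r does rise. A reader might infer that the clause passes equally often under any drug effect. That holds for the mean effect only. But a spread of effects with no average benefit raises r just as much, so the clause still does not show that the drug works.
- *The d > 0.48 clauses guard the criterion.* They do respond to the drug, so it would be wrong to infer that the whole criterion ignores it. But they concern desire alone and do not show that reaction time, EEG or gaze follows the drug's effect. The mixed connectives also leave unclear whether they are always required.
- *Part of the remedy is already planned.* This stands for reaction time and gaze, where the ANOVA supplies treatment-by-time terms, and Section 4 makes EEG change from baseline the primary outcome. None of this is connected to the r clauses.

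**Conclusion.** The point holds for the reaction-time clause. Taken within the flibanserin arm, r > 0.48 passes about 5%, 51% or 91% of the time according to rho (0.30, 0.48, 0.60) and regardless of the mean drug effect. Taken as a difference of correlations, it passes about 0.3% of the time or less over that range of rho (0.6% or less if rho = 0 is included) under a uniform effect, and 0.2% or less under a fully mediated one, which is the case the trial hopes for. Taken as a pooled r, it moves with the drug but passes about 1%, 50% and 97% of the time with an inert one. For EEG and gaze the point is conditional on what change in flibanserin means.

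The size depends on rho, which the documents do not give. That the within-arm r is unchanged by the mean effect is algebra and does not depend on rho. This is more than missing detail, because on its most natural reading a stated success threshold can give the wrong signal.

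**What to change.** Stop using r > 0.48 as a success criterion. To claim that a reaction-time, EEG or gaze measure goes with the drug's effect on desire, require all three of:

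1. a flibanserin-placebo difference in change in desire, in the beneficial direction;
2. a flibanserin-placebo difference in change in that measure, from the treatment-by-time term already planned for reaction time and gaze, and from the same contrast for EEG;
3. a slope of change in desire on change in that measure, with arm in the model, whose sign agrees with (1) and (2).

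Report the correlation in each arm, and their difference, with 95% confidence intervals as description. Replace change in flibanserin with the measured variable intended. An indirect effect with a bootstrap interval may be added as exploratory, but must not carry the claim alone, for the reason in Step 6 of the working.

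The cost is SAP wording and a little extra analysis of data already planned. The downside is that the slope in (3) is not protected by randomisation, so the association claim should be labelled exploratory.
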